Encouraging Overdue Healthcare Appointment Scheduling
Among Patients with Chronic Diseases

Statistical Analysis Plan

August 2, 2021

Statistical Analysis Plan

Brief Summary

The goal of this study is to determine the most effective messages for encouraging patients with chronic conditions, who have not seen their doctor in at least one year, to return to the clinic. Study participants will receive postcards or letters encouraging them to make an appointment. Researchers will assess whether messages increase appointment scheduling (and attendance).

Study Populations

This study includes four distinct populations: 1. **Medicaid** patients (pending approval of study materials for this population), 2. Geisinger Health Plan (GHP) members who are also Geisinger patients (**patient-members**), 3. GHP **members** only, and 4. Geisinger **patients** only.

It is important to note these distinct populations because appointment scheduling data (our primary outcome) are available only for patients and patient-members. Patient and patient-member data will be analyzed together in this study. Data for members and Medicaid patients (if available) will be included as separate subsamples in the study.

Project Status

The study design is finalized, and mailers were sent to patients, patient-members, and members, but data have not yet been extracted or analyzed as of the time this document was uploaded.

A sample of Medicaid patients may also be included, pending approval of study materials for this population.

Power Analysis

At baseline, an estimated 10% of patients may schedule appointments. The study will achieve 80% power to observe about a 3.1% absolute increase (or a 31% relative increase) in scheduled appointments in any of the intervention arms, relative to the control arm, at a two-tailed $p < .05$ with $n = 1,643$ patients per arm. A primary outcome analysis compares data from the control arm to combined experimental arms. Therefore, the sample described below will allow power to detect an even smaller effect for this analysis.

Estimated Sample Sizes

Geisinger patients/patient-members, GHP members, and Medicaid patients (if approved) will be randomly assigned to 1 of 4 arms. Estimated enrollment for each subsample and arm is listed below, with intervention arms highlighted in blue:

Arm	Patients/ Patient-members	Members	Medicaid
1. Standard Outreach Postcard	1,643	2,163	~794
2. Humorous Postcard	1,643	2,163	~794
3. Physician Letter	1,643	2,163	~795

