4. Control	1,643	2,163	~795
Total	6,572	8,652	3,182

Study Timeline

Mailers were sent to patients, patient-members, and members in late July, 2021 across 3 drop dates. Mailers from each arm were evenly divided, at random, across the dates.

If materials for Medicaid patients are approved, this subsample will receive modified versions of the mailers in late 2021 (drop dates TBD), and data will be included in analyses of secondary outcomes.

Planned Analyses

Analyses will test whether participants in any of the study arms are more likely to schedule or attend appointments relative to those in a no-contact control arm.

Primary analyses will test whether Geisinger patients or patient-members who receive mailers are more likely to schedule an appointment relative to those in the no-contact control arm.

Secondary analyses will assess the following:

- Whether patients or patient-members who receive mailers are more likely to attend an appointment that they scheduled during the study period, relative to control
- The relative efficacy of different mailers in increasing appointment scheduling
- The relative efficacy of different mailers in increasing appointment attendance
- Whether appointments occur sooner in mailer groups relative to control

Analyses will include a series of generalized linear models (GLMs) specifying a binary outcome and log-link function for scheduling and attendance, and a negative binomial distribution and log-link function—or another distribution and link function if better suited to the data—for appointment timing. All analyses will be run in R.

Planned outcomes and comparisons of interest are detailed below.

Notes about timeframes and analysis

Mailers were sent on 3 different drop dates. Timeframes listed below refer to the amount of time elapsed from the drop date for a given participant. For instance, the primary outcome timeframe is 30 days; thus, for the purposes of this study, a patient will be counted as having scheduled an appointment if there was an appointment scheduled in the 30 days following that patient's drop date.

Control participants will be separated into 3 drop date groups, each assigned to one of the three drop-date groups for the experimental arms. Each control group will be monitored for appointments during a date range that is aligned with that for its corresponding experimental group.

Outcomes

Primary outcome:

1. Patients – Appointment scheduling – 30 days – confirmatory

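### The primary scheduling model is specified by outcome, link and arm contrasts only, which leaves unused a modest precision gain from baseline information the sponsor holds

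*SAP*

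**What the plan says.** **Model.** SAP, Planned Analyses: "Analyses will include a series of generalized linear models (GLMs) specifying a binary outcome and log-link function for scheduling and attendance". The same sentence allows another distribution and link, but only for appointment timing. The primary outcome in the Outcomes section is 30-day scheduling among patients, with two sets of contrasts: each mailer vs control, and all mailers combined vs control. No covariate or stratification term is named, and the SAP does not call the model unadjusted.

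**Baseline information.**
- Study Populations lists patients and patient-members as separate populations, then states: "Patient and patient-member data will be analyzed together in this study".
- Brief Summary describes the target group as those "who have not seen their doctor in at least one year". Time since last visit appears only as this threshold.
- Study Timeline says of the drop dates: "Mailers from each arm were evenly divided, at random, across the dates". The notes on timeframes add that controls will be split into three groups aligned with those dates.

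**Power.** SAP, Power Analysis: "At baseline, an estimated 10% of patients may schedule appointments". It continues: "The study will achieve 80% power to observe about a 3.1% absolute increase (or a 31% relative increase) in scheduled appointments", "at a two-tailed $p < .05$ with $n = 1,643$ patients per arm".

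**The concern.** In a randomised comparison, adjusting for baseline variables that predict the outcome reduces residual variance and so narrows the interval for the arm effect. The sponsor knows patient status for all 6,572 people in the primary sample. It must have applied some last-visit criterion to select them. Both could plausibly predict booking, yet neither enters the model as written.

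What is at stake is a little precision in the confirmatory contrasts, and clarity. According to Project Status, data had not been extracted when the SAP was uploaded. Terms named at that stage are prespecified; terms chosen after extraction are open to the charge of selection. The estimator also matters once covariates enter. A log-binomial model with a continuous covariate can fail to converge, and the SAP gives no fallback for scheduling.

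**Working it through.** **Inputs from the SAP.** Control rate 10%, mailer rate 13.1%, n = 1,643 per arm, two-sided alpha 0.05. R² is not in the SAP and is assumed below.

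**1. The plan's own figure.** Pooled normal approximation, with p̄ = (0.100 + 0.131)/2 = 0.1155:
- SE under the null = √[2 × 0.1155 × 0.8845 / 1,643] = 0.01115
- SE under the alternative = √[(0.10 × 0.90 + 0.131 × 0.869) / 1,643] = 0.01114
- Power = Φ[(0.031 − 1.96 × 0.01115) / 0.01114] = 79.4%

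The unpooled form gives 79.5% and the arcsine form 79.6%. Power is exactly 80% at a difference of 3.12 points, which rounds to 3.1, so the stated figure reproduces. For combined mailers vs control (4,929 vs 1,643), power at 3.1 points is 92.4% and the detectable difference is 2.55 points.

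**2. Effect of adjustment.** Multiply the variance by (1 − R²), so that both SEs shrink by √(1 − R²). Pooled form, each mailer vs control:

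| Assumed R² | Power at 3.1 points | Detectable difference (points) |
|---|---|---|
| 0 | 79.4% | 3.12 |
| 1% | 79.8% | 3.11 |
| 2% | 80.2% | 3.09 |
| 3% | 80.6% | 3.07 |
| 5% | 81.4% | 3.04 |
| 6% | 81.8% | 3.02 |

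At R² = 6%, √0.94 = 0.970, so intervals narrow by about 3%.

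**3. What R² is plausible?** All rates here are assumptions.

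*Time since last visit.* Take 40/35/25% of patients in three bands, with an overall rate of 10%. R² is the between-band variance divided by 0.10 × 0.90. For rates of 13/9/6.6%, the between-band variance is 0.40 × 0.030² + 0.35 × 0.010² + 0.25 × 0.034² = 0.000684, and 0.000684 / 0.09 = 0.8%.

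| Rates by band | R² | Power at 3.1 points | Equivalent extra patients per arm, 1,643/(1 − R²) − 1,643 |
|---|---|---|---|
| 13/9/6.6% | 0.8% | 79.7% | 13 |
| 15.5/7.5/4.7% | 2.4% | 80.4% | 40 |
| 19/5/2.6% | 6.1% | 81.9% | 107 |

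The last row needs about a seven-fold gradient (19/2.6 = 7.3).

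*Patient status.* With a 50/50 split, rates of 9% vs 14.1% give R² = (0.0255)² / (0.1155 × 0.8845) = 0.6%. Rates of 6% vs 17.1% give 3.0%.

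*Drop date.* Three dates with rates one or two points apart (middle date at the mean) give R² of (2/3 × 0.01²)/(0.1155 × 0.8845) = 0.07% or, with 0.02, 0.26%.

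**4. Simulation check.** 4,000 trials per scenario, linear risk-difference model with robust SE, with and without a binary and a continuous baseline term. With no prognostic value, power changed by about 0.1 point, so no penalty was seen. Variance reductions of 1.0%, 4.2% and 7.9% raised power by 0.5, 1.4 and 2.6 points.

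**The case against.** The SAP is silent on adjustment rather than wrong. An arm-only comparison in a randomised sample of 6,572 is valid, and the gain rests on assumed booking rates, with zero inside the range. Only patient status is clearly known for everyone. The convergence risk is also largely created by adding covariates. All of this stands, and it limits the point to a modest, optional improvement.

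Three stronger readings might be inferred; the document supports none of them.
- *The trial falls short of 80% power because covariates are left out.* The 0.6-point gap at exactly 3.1 points comes from rounding 3.12 to a figure the SAP qualifies as approximate. It concerns only the individual-mailer contrasts.
- *Drop date is a randomisation block that the model must respect.* The SAP describes mailers of each arm being spread over the dates. It does not describe randomisation to arms within dates, and control groups are still to be formed. Drop date is balanced across mailer arms by construction and would add almost no precision.
- *A continuous time since last visit is held for everyone.* The one-year threshold makes this likely for the sponsor's own patients, but the SAP does not say so.

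**Conclusion.** The point holds as a small efficiency and prespecification matter. As written, the confirmatory model uses arm alone and leaves available baseline information unused. For an assumed R² of 0 to 6%, adjustment raises power for each mailer vs control at 3.1 points from 79.4% to about 82% and lowers the detectable difference from 3.12 to about 3.02 points. The upper end needs a steep booking gradient over time since last visit, and that variable to be held as a value. The estimates also assume that adjustment scales the variance by (1 − R²). The power statement needs no correction, and the arm-only analysis would not be biased.

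**What to change.** Before data extraction, specify the primary scheduling model as arm + patient vs patient-member status + time since last visit at the drop date, the last term only if it is held as a value. Drop-date group may be added as an optional design term, with almost no precision expected from it. If it is used, state how controls are assigned to the three groups, preferably at random.

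Estimate the risk ratio by Poisson regression with robust variance or by standardised logistic regression. Either keeps the risk-ratio scale implied by the log link and avoids log-binomial convergence failure. Keep the arm-only model as a sensitivity analysis. If the sponsor prefers arm-only as primary, say so explicitly. If the protocol already names covariates, carry them into the SAP.

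Cost: a few lines of SAP text, slightly more code, and a change of estimator from plain log-binomial. No extra patients are needed.

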 - a. individual mailers vs. control
 - b. mailers combined vs. control

Secondary outcomes:

1. Patients – Appointment scheduling – 30 days – exploratory
 - a. outreach vs. humorous vs. letter
2. Patients – Attendance at appointments scheduled within 30 days of mailers – 180 days – exploratory
 - a. individual mailers vs. control

- b. mailers combined vs. control
- 3. Patients, Members, & Medicaid – Attendance at any appointment – 30 days – exploratory
 - a. individual mailers vs. control
 - b. mailers combined vs. control
 - c. outreach vs. humorous vs. letter
- 4. Patients, Members, & Medicaid – Attendance at any appointment – 90 days – exploratory
 - a. individual mailers vs. control
 - b. mailers combined vs. control
 - c. outreach vs. humorous vs. letter
- 5. Patients, Members, & Medicaid – Attendance at any appointment – 180 days – exploratory
 - a. individual mailers vs. control
 - b. mailers combined vs. control
 - c. outreach vs. humorous vs. letter
- 6. Patients, Members, & Medicaid – Timing of appointment – 30 days – exploratory
 - a. individual mailers vs. control
 - b. mailers combined vs. control
 - c. outreach vs. humorous vs. letter
- 7. Patients, Members, & Medicaid – Timing of appointment – 90 days – exploratory
 - a. individual mailers vs. control
 - b. mailers combined vs. control
 - c. outreach vs. humorous vs. letter
- 8. Patients, Members, & Medicaid – Timing of appointment – 180 days – exploratory
 - a. individual mailers vs. control
 - b. mailers combined vs. control
 - c. outreach vs. humorous vs. letter

Additional outcomes:

- 1. Patients – appointment scheduling within 14 days of mailers being sent – exploratory*
 - a. outreach vs. humorous vs. letter
- 2. Patients – Calls to appointment scheduling – 30 days – exploratory
 - a. individual mailers vs. control
 - b. mailers combined vs. control
 - c. outreach vs. humorous vs. letter

*Note: this analysis will inform internal operations but will not be reported in publication.

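### The timing outcomes (secondary outcomes 6–8) have a model but no rule for people without an appointment in the window, who are most of the sample at 30 days

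*SAP*

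**What the plan says.** Under Planned Analyses, one secondary question is "Whether appointments occur sooner in mailer groups relative to control". The outcome list turns it into three outcomes at 30, 90 and 180 days, the first being "Patients, Members, & Medicaid – Timing of appointment – 30 days – exploratory". Each is compared for individual mailers against control, for mailers combined against control, and between mailers.

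The model is a GLM with "a negative binomial distribution and log-link function—or another distribution and link function if better suited to the data—for appointment timing".

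The notes on timeframes start the clock at each participant's drop date. They also give follow-up for controls: "Each control group will be monitored for appointments during a date range that is aligned with that for its corresponding experimental group". For scheduling they give a rule that classifies every patient: "a patient will be counted as having scheduled an appointment if there was an appointment scheduled in the 30 days". There is no matching rule for timing. Nothing says whether a person with no appointment in the window is left out, given a value or censored.

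Study Populations adds that "appointment scheduling data (our primary outcome) are available only for patients and patient-members". Timing for members and Medicaid patients must therefore rest on attended visits.

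**The concern.** The SAP fixes the family, link, time origin, windows and contrasts for timing, so the analysis set and the handling of people without a visit belong in the same specification. The clause allowing a better-suited distribution or link does not settle this. No distribution for days supplies a value for someone who has no day.

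A negative binomial model for days has no censoring mechanism, so the likely (though unstated) reading is that it is fitted to people with an observed appointment. Attending is what the mailers are meant to change, so attenders in the mailer and control arms are no longer randomised groups. If mailers bring in extra people, the mean day among attenders moves towards whenever those people happen to come. A mailer that delays nobody could then be reported as making appointments later, beside an attendance result for the same window ("Patients, Members, & Medicaid – Attendance at any appointment – 30 days – exploratory") showing that more people were seen.

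Another reading the SAP equally permits is the smaller of days and window length in everyone. That reading keeps the randomised groups. The two can point in opposite directions on the same data.

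**Working it through.** **1. The SAP's own figure.** The SAP gives no figure for timing, so the check starts from its power statement: 10% control, a 3.1-point increase, 1,643 per arm, two-sided 0.05, 80% power.

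n = [1.960·√(2·0.1155·0.8845) + 0.842·√(0.10·0.90 + 0.131·0.869)]² / 0.031² ≈ 1,668 per arm.

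Power at 1,643 is 0.794. The figure reproduces.

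**2. How many people have no day to analyse.** Use 10% and 13.1% as a proxy for attendance by day 30.
- Control: 1,643 × 0.10 ≈ 164 with a day, 1,479 (90%) without.
- Each mailer arm: 1,643 × 0.131 ≈ 215 with a day, 1,428 (87%) without.

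If the same daily hazards continue, the shares without a day (control/mailer) are 73%/66% at 90 days and 53%/43% at 180 days.

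**3. Scenarios (assumed, not in the SAP).** The control daily hazard is −ln(0.9)/30 = 0.00351. In the mailer arm the added cumulative hazard is −ln(0.869) + ln(0.9) = 0.1404 − 0.1054 = 0.0351. It is spread evenly over stated days so that 13.1% attend by day 30. Alternatively, a sustained hazard ratio of 0.1404/0.1054 = 1.33 applies. In every scenario mailers only add visits.

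With S(d) the proportion not yet seen by day d, P(d) = S(d−1) − S(d), and p the proportion seen by the window end T:
- attenders-only mean: m = Σ d·P(d) / p
- capped mean in everyone: p·m + (1 − p)·T

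The control attenders-only mean at T = 30 is 15.24 days. The control capped mean is 0.10 × 15.24 + 0.90 × 30 = 28.52.

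| Extra visits fall on | Attenders-only mean | Difference from 15.24 | Ratio | Capped ratio, everyone |
|---|---|---|---|---|
| days 3–14 | 13.42 | −1.82 | 0.881 | 0.976 |
| sustained | 15.15 | −0.09 | 0.994 | 0.984 |
| days 7–30 | 15.91 | +0.67 | 1.044 | 0.987 |
| days 10–30 | 16.29 | +1.05 | 1.069 | 0.989 |
| days 14–30 | 16.79 | +1.55 | 1.102 | 0.991 |

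Example, days 14–30, capped: 0.131 × 16.79 + 0.869 × 30 = 28.27, and 28.27/28.52 = 0.991.

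A third possible reading, coding non-attenders as 0, gives ratios of 1.15 to 1.44.

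**4. How often this would be declared significant.** Simulation: 1,500 trials per scenario, 1,643 per arm, two-sided 5%. The negative binomial model is fitted to attenders only, and each range runs from model-based to robust standard error. The comparator is a discrete-time complementary log-log GLM on person-days in everyone, with 10-day baseline blocks.

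| Extra visits fall on | Attenders-only negative binomial | Complementary log-log: hazard ratio, significant sooner |
|---|---|---|
| days 3–14 | sooner 47–55% | 1.34, 79% |
| sustained | sooner 1–3% | 1.33, 77% |
| days 7–30 | later 8–12% | 1.33, 76% |
| days 10–30 | later 17–23% | 1.32, 75% |
| days 14–30 | later 30–40% | 1.32, 75% |

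With no effect, the attenders-only model gives sooner/later in 1.1%/1.4% (model-based) or 2.1%/2.9% (robust), so the later results are not a test-size artefact. The complementary log-log model was never significant for later. A plain two-proportion test of attendance is significant in about 77%.

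**5. The longer windows.** Attenders-only ratios at 90 and 180 days are 0.906 and 0.937 (days 3–14), 0.982 and 0.962 (sustained), and 0.932–0.941 and 0.945–0.948 (the three late cases). The 30-day reversal does not carry over. A hazard ratio of 1.33 confined to days 31–90 gives 1.053 at 90 days (significant later in 18–29%) and 0.955 at 180.

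**6. Other base rates.** For control rates from 5% to 20% (5% against 6.55% or 7.35%; 20% against 24% or 26.2%), the 30-day attenders-only ratios are 0.85–0.91 (days 3–14), 0.99–1.00 (sustained) and 1.07–1.14 (days 14–30).

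**The case against.** The SAP is silent; it does not commit to the attenders-only analysis. Under the capped reading the direction is right in all five 30-day scenarios. A later result needs the extra visits to be placed late, and at 30 days it is contradicted by outcomes 7 and 8 in the same scenarios. The inputs are proxies: the 10% is a scheduling rate with no stated window, nothing is given for members or Medicaid patients, and the longer windows extrapolate a hazard that puts about 47% of controls at a visit by day 180. All three outcomes are exploratory, and outcomes 3–5 already show whether more people came. One sentence on the analysis set would close the gap. A complementary log-log model is one choice among several, and at 30 days it nearly duplicates the attendance test.

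Most of this stands as a limit on severity and on how literally to take the percentages. It does not remove the gap. The missing rule covers most records at 30 days whatever the exact rates, and the reading that can reverse direction is the one a count model for days most naturally invites. That the capped reading behaves well is a reason to state a rule that keeps everyone. The point about the remedy is partly right: the essential change is the rule, and the particular model is secondary.

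**Conclusion.** The point holds. For timing outcomes 6–8 the SAP names a model without saying what people with no appointment in the window contribute, which on its own rates is 87–90% of records at 30 days. Fitted to attenders only, the 30-day ratio ranges from 0.88 to 1.10 in scenarios where mailers delay nobody. A significant later result occurs in 8–40% of trials when the extra visits come late in the window.

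These sizes rest on scheduling rates standing in for attendance, assumed visit timing, a constant control hazard and 1,643 per arm. The gap itself rests on none of them.

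Severity is minor to moderate. The plan should be changed, but the confirmatory 30-day scheduling analysis and its power are unaffected.

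**What to change.** For outcomes 6–8, state that timing is days from the assigned drop date to first attended appointment, in all randomised people, censored at the end of the 30-, 90- or 180-day window. Name one model in advance. A discrete-time complementary log-log GLM handles the censoring and stays within the planned GLM framework. Show cumulative incidence by arm, and label any comparison among attenders only as descriptive. The three windows can stay.

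The cost is a few lines of text and standard R code. Visit and drop dates are needed anyway, and controls already have aligned monitoring periods. When the SAP was posted, "data have not yet been extracted or analyzed as of the time this document was uploaded", so the rule could be set without sight of results.

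There are two drawbacks. Timing results will partly overlap attendance, mostly at 30 days (75–79% significant against 77%). If extra visits come early, the complementary log-log model is significant less often than the attenders-only model: 43% against 49–64% at 90 days, and 28% against 33–49% at 180 days.

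### Does the plan need to say whether the exploratory three-mailer comparison is one overall test or three pairwise tests?

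*SAP*

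**What the plan says.** The Brief Summary opens with the aim: "The goal of this study is to determine the most effective messages for encouraging patients with chronic conditions". Planned Analyses lists among the secondary analyses "The relative efficacy of different mailers in increasing appointment scheduling", and describes the model: "Analyses will include a series of generalized linear models (GLMs) specifying a binary outcome and log-link function for scheduling and attendance".

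Under Outcomes, the direct comparison of mailers on 30-day scheduling is Secondary outcome 1a, labelled exploratory and written as "outreach vs. humorous vs. letter". The same phrase is used in Secondary 3c to 8c and in Additional 1a and 2c, which makes nine places, all exploratory. No contrast, overall test, threshold or adjustment is attached to any of them.

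The one significance level in the SAP is in Power Analysis and concerns a mailer against control: "relative to the control arm, at a two-tailed $p < .05$ with $n = 1,643$ patients per arm". The confirmatory analyses, under Primary outcome, are each mailer against control and all mailers pooled against control.

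**The concern.** The phrase fits two analyses. One is a single 2-df test of whether the three arms differ at all, which does not say which mailer is better. The other is three pairwise tests, which do say so but, if unadjusted, carry a familywise error above 5%. The SAP does not choose, so the choice could be made after the data are seen. The same data could then support either no difference or a better mailer.

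This looked important because the stated aim is to find the most effective messages, and this comparison is the one that sets the mailers directly against each other. In addition, the note under Additional outcomes says of one such comparison that "this analysis will inform internal operations but will not be reported in publication", so a decision may rest on a result of this kind.

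**Working it through.** **Inputs.** From the SAP: 1,643 patients or patient-members per arm, two-sided .05, 10% baseline scheduling and a 3.1-point detectable increase. The mailer-arm rates are assumptions; 13.1% is the baseline plus the detectable increase.

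**The plan's own figure first.** For 10% against 13.1% the mean rate is p̄ = 0.1155, and

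power = Φ{[0.031·√1643 − 1.96·√(2·0.1155·0.8845)] / √(0.10·0.90 + 0.131·0.869)}
= Φ[(1.2566 − 0.8859) / 0.4515] = Φ(0.821) = 79.4%.

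The stated 80% is reproduced.

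**Can the readings differ?** Take illustrative counts of 197, 215 and 238 out of 1,643 (12.0%, 13.1%, 14.5%).

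- Overall test: the expected count per arm is 650/3 = 216.67 and the pooled rate is 0.1319. The statistic is Σ(x − 216.67)² / [216.67·(1 − 0.1319)] = 844.67/188.09 = 4.49 on 2 df, p = 0.106.
- First against third mailer: the pooled rate is 435/3286 = 0.1324. Then z = (41/1643)/√(0.1324·0.8676·2/1643) = 2.11, p = 0.035. The other two pairs give p = 0.34 and p = 0.24.

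So they can differ.

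**How often do they differ?** Simulated trials with 1,643 per arm, a 2-df chi-square test at .05, and three pooled two-proportion tests at .05 each:

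| Assumed rates (%) | Overall test significant | Any pair significant | Readings disagree |
|---|---|---|---|
| 13.1 / 13.1 / 13.1 | 5.0% | 12.2% | 7.2% |
| 13.1 / 13.1 / 15.1 | 38% | 54% | 16% |
| 13.1 / 13.1 / 16.2 | 75% | 85% | 10.5% |

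With identical mailers the first row is nearly the same at common rates of 10% and 15%. Every disagreement was a significant pair beside a non-significant overall test; the reverse did not occur.

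**Does the choice affect which mailer is called best?** Count a mailer as best only if it beats both others, each at .05. Compare unadjusted pairs with pairs read only after a significant overall test:

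| Assumed rates (%) | Event | Unadjusted pairs | Overall test first |
|---|---|---|---|
| 13.1 / 13.1 / 13.1 | a false winner is named | 1.3% | 1.2% |
| 13.1 / 13.1 / 15.1 | the true best is named | 21.9% | 21.3% |
| 13.1 / 13.1 / 16.2 | the true best is named | 57.0% | 56.4% |

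The largest gap here is 57.0 − 56.4 = 0.6 points. Separate simulation runs differ by about 0.1 to 0.2 points. The 12.2% and the 1.3% describe different events: any one significant pair, and one mailer ahead of both others.

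**The case for a change.** The best case for a change is that naming the comparison is the SAP's own job, that the phrase leaves it open in nine places, and that a few lines would settle it while the data are still unextracted. An exploratory label excuses the lack of strict error control, but it does not tell the analyst which test to run. With three arms, an overall test followed by pairwise tests at .05 is a closed procedure. It would hold the false-difference rate at 5% at almost no cost in naming the best mailer.

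Much of this stands. The ambiguity is real, the figures reproduce, and an author who added a clarifying line would do no harm. Three parts do not carry the weight placed on them.

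- The 12.2% counts any significant pair. For the event that matches the aim, one mailer ahead of both others, unadjusted pairs give 1.3%.
- The note about internal operations is tied by its asterisk to Additional outcome 1, the 14-day analysis that will not be published. Nothing says that Secondary 1a will drive operations.
- The two-step rule controls error only within one outcome and one subsample. Secondary 3c to 8c cover three populations, which gives 6 × 3 = 18 families. Secondary 1a and Additional 1a and 2c bring this to 21. A rule applied within each would still leave them uncontrolled together, which is usual for exploratory work.

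**Conclusion.** No change to the plan is needed. The wording leaves a detail open in outcomes that are all labelled exploratory. Both readings are acceptable there, and whether to gate or adjust exploratory pairwise contrasts is a matter on which reasonable statisticians differ. A log-link model with arm as a factor yields the overall test and the three pairwise risk ratios from the same fit, so an analyst can report both and say that the pairs are unadjusted. A reader can then discount a lone p < .05.

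The confirmatory comparisons with control are unaffected, and no stated figure is wrong. The readings disagree on whether any difference exists in about 7% of trials with identical mailers and in 10.5% to 16% under the differences tabulated above. They differ by at most 0.6 points on whether one mailer beats both others.

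These sizes rest on assumed mailer rates of 13.1% to 16.2% (10% to 15% for identical mailers) and on chi-square and z-tests in place of the log-link model, which should be nearly equivalent at this sample size. Nothing was computed for the appointment-timing outcomes.
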